#### **4.4.2 Primary Efficacy Analysis**

The efficacy analysis will be conducted all consented treated subjects with a 5+ year study visit. Results will be reported for observed data only; missing values will not be imputed.

The primary analysis will test the mean improvement in ODI from baseline to 5+ years as an intra-patient comparison. The mean change will be analyzed with an ANCOVA with a covariate of baseline ODI score. See Appendix A - Table 8.

If  $p \leq 0.05$  then it may be concluded that a significant functional improvement was demonstrated in axial low back pain subjects treated with the Intracept procedure and that the treatment is durable to mean follow-up for the long term study.

A comparison will be made between the ITT (as treated cohort) and a Intracept only treated cohort (with those subjects that had additional procedures such as RF Ablation, microdiscectomy, fusion, etc. removed).

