6 STATISTICAL ANALYSIS

6.1 Statistical Methods

Demographic and baseline characteristics will be summarized using descriptive statistics.

The mean change from baseline to five years in the ODI is the primary endpoint for this study. Statistical differences will be tested using Student's t-test. An analysis of covariance will also be performed using baseline characteristics and ODI measurements.

Secondary endpoints will be summarized using descriptive statistics.

- Mean reduction in pain rating baseline to 5+ years.
- Responder rates for ODI will be determined by the proportion of subjects who achieve \geq 10-point reduction in ODI from baseline to 5+ years post-treatment.
- Responder rates for pain rating will be determined by the proportion of subjects who achieve a \geq 1.5-point reduction in pain rating from baseline to 5+ years post-treatment.

- Number and rate of surgical interventions post-procedure, as adjudicated by an independent reviewer.
- The proportion of patients currently utilizing opioids for low back pain of the same treatment region.
- The proportion of patients utilizing injections in the past 12 months for low back pain of the same treatment region.
- Patient satisfaction with the Intracept Procedure at 5+ years.

No imputations will be made for missing data.

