#### **4.3 Adjustments for Covariates**

Baseline ODI score will be a covariate for the primary efficacy endpoint. The respective baseline value will be used as covariate in the secondary efficacy endpoints for VAS. No other planned analyses will include covariates.

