##### **4.4.3.2 Pain Score**

The mean change will be analyzed with an ANCOVA with a covariate of baseline VAS score. See Appendix A - Table 9.

Responder rates for numeric pain scores (VAS scale 0 to 10) will be determined by the proportion of subjects who achieve  $\geq 1.5$  and  $2.0$  point reductions in pain score from Baseline to 3 months.

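### SAP 4.4.2 drops the protocol's t-test for the primary ODI change and ties p ≤ 0.05 to a one-group ANCOVA without saying which term or contrast supplies the p-value

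*SAP*

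**What the plan says.** Protocol 6.1, on the primary endpoint: "Statistical differences will be tested using Student's t-test". It then adds a second analysis: "An analysis of covariance will also be performed using baseline characteristics and ODI measurements".

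SAP 4.4.2 states the aim: "The primary analysis will test the mean improvement in ODI from baseline to 5+ years as an intra-patient comparison". The only method it names is this: "The mean change will be analyzed with an ANCOVA with a covariate of baseline ODI score". SAP 4.3 agrees: "Baseline ODI score will be a covariate for the primary efficacy endpoint". The t-test no longer appears in the primary analysis, and no reason is given.

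The decision rule in SAP 4.4.2 is that, if p ≤ 0.05, "it may be concluded that a significant functional improvement was demonstrated in axial low back pain subjects treated with the Intracept procedure", and also that the effect is durable. SAP 4.1 makes tests two-sided at 0.05. SAP Table 8 has one p-value slot in the row for mean ODI change and names no model term, contrast or covariate centring.

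For pain, SAP 4.4.3.2 uses the same model: "The mean change will be analyzed with an ANCOVA with a covariate of baseline VAS score". No success rule is attached to it. Protocol 6.1 plans only descriptive statistics for the secondary endpoints, pain included.

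**The concern.** SAP 3.1.1 defines the endpoint within treatment-arm subjects, so the model has no group factor. It reduces to change = a + b × baseline ODI, and standard output gives two p-values:

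- The intercept p-value tests the predicted change for a patient whose baseline ODI is 0, far outside the trial population.
- The slope (or model F) p-value tests whether change depends on baseline. Regression to the mean alone can make it small.

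Neither tests whether the mean change is zero. A third quantity, the fitted change at the average baseline, does, but it must be requested or obtained by centring. The study's only success rule therefore depends on a choice the SAP leaves open. Two of the three candidates could miss a large real improvement or declare one where none exists.

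**Working it through.** **Inputs.** The documents give no sample size calculation, SD or correlation for this study, so there is no planned figure to reproduce. The illustration uses:

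- Mean change −23.4 ODI points (24-month figure, Protocol 2 and SAP 1).
- Baseline mean about 23.4 / 0.537 = 43.6. This is approximate, because a mean of percentages is not a ratio of means.
- Assumed: n = 100 (at most 133 are eligible), SD of change 18, baseline SD 8 to 12, slope b from −0.3 to −0.8.

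**Formulas.**

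- Paired t = mean change / (18/√n).
- Residual SD: s = √(18² − (b × SD_base)²).
- Intercept: a = −23.4 − b × 43.6, with SE = s × √(1/n + 43.6²/((n−1) × SD_base²)).
- Slope SE = s / √((n−1) × SD_base²).
- LS mean at the average baseline: estimate −23.4, SE = s/√n. Its ratio to the correct SE is s/18, and approximate coverage of a nominal 95% CI is 2Φ(1.96 × s/18) − 1.

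**One case in full** (SD_base 10, b = −0.5). Paired t = −23.4/1.8 = −13.0. s = √(324 − 25) = 17.29. The intercept is −23.4 + 21.8 = −1.6 with SE 7.77, so p = 0.84. The slope is −0.5 with SE 0.174, so p = 0.005. The LS-mean SE is 1.73, ratio 0.96, coverage 94.0%.

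**All nine cases.**

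| SD_base | b | Intercept (p) | Slope p | LS-mean SE ratio | Coverage |
|---|---|---|---|---|---|
| 8 | −0.3 | −10.3 (0.30) | 0.18 | 0.99 | 94.8% |
| 8 | −0.5 | −1.6 (0.87) | 0.026 | 0.98 | 94.4% |
| 8 | −0.8 | +11.5 (0.22) | <0.001 | 0.93 | 93.3% |
| 10 | −0.3 | −10.3 (0.20) | 0.096 | 0.99 | 94.7% |
| 10 | −0.5 | −1.6 (0.84) | 0.005 | 0.96 | 94.0% |
| 10 | −0.8 | +11.5 (0.12) | <0.001 | 0.90 | 92.1% |
| 12 | −0.3 | −10.3 (0.13) | 0.045 | 0.98 | 94.5% |
| 12 | −0.5 | −1.6 (0.80) | <0.001 | 0.94 | 93.5% |
| 12 | −0.8 | +11.5 (0.049) | <0.001 | 0.85 | 90.3% |

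The paired t is −13.0 throughout. The slope p-value does not involve the mean change. The one intercept p-value below 0.05 belongs to a positive intercept, the direction of worsening.

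**Simulation.** Assumed baseline SD 10 to 14, follow-up SD 16 to 18, correlation 0.2 to 0.6; 1,000 to 2,000 runs per scenario. Share of runs with p ≤ 0.05:

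| Test | True change 0 (n = 100, 133) | True change −23.4 (n = 60, 100, 133; SDs 10 and 16) |
|---|---|---|
| One-sample t-test | 4.1–6.1% | 100% |
| LS mean at average baseline | 4.2–11.6% | 100% |
| Uncentred intercept | 5–100% | 12–99% |
| Baseline slope | 4–100% | 5–100% |

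With true change 0, n = 100, SDs 10 and 16 and correlation 0.2, the slope was significant in 98.8% of runs and the uncentred intercept in 98.4%. The LS mean was significant in 7.6% and the t-test in 5.0%. The LS-mean excess peaks at baseline SD 14 and correlation 0.2. It arises because the variance of the mean change is s²/n plus b² × SD_base²/n, and the model-based SE drops the second part.

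**When would the LS mean and the t-test disagree?** With n = 100 and SD 18, the t-test needs an observed mean change of 1.984 × 1.8 = 3.6 points. In the most extreme of the nine cases the LS mean needs 1.984 × 1.523 = 3.0 points. Only a result between those values would change the decision, well below the 10-point clinically important difference in Protocol 7.1.

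**The case against.** A reader might infer that the primary rule rests on the wrong test. The documents do not support that. SAP 4.4.2 says the hypothesis is the mean within-patient improvement, Table 8 puts the p-value in the mean-change row, LSMean is a listed abbreviation, and the parent trial's ODI result was reported as LS means. The sensible reading is the LS mean at average baseline, which targets the right quantity. The intercept and slope figures above describe what could go wrong if an analyst took the wrong line of output; they are not the plan. All of this stands.

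It also stands that zero-change tests exist elsewhere. SAP Table 10 plans an rm F-test of zero ODI change at 5+ years, and a t-test of zero VAS change, each with a 95% CI. They are supplemental (SAP 4.4.3.3, which cites the table as Table 11), so they do not settle the primary rule. They do show that the SAP can state the null explicitly, and for ODI they add a further test of the same quantity.

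A reader might also infer that the protocol requires a t-test for pain, or that a success claim for pain is at risk. Neither holds: Protocol 6.1 plans description only, and the p ≤ 0.05 rule concerns ODI. Nor does the protocol use the word paired, although in a single arm with a within-patient endpoint no other reading is natural.

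The objection does not remove two things. The SAP never links LSMean to the primary p-value. And even the favourable reading gives error bars that are somewhat too narrow, while in a single arm the adjustment leaves the estimate unchanged.

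**Conclusion.** The point holds as a discrepancy and a gap in specification. SAP 4.4.2 drops the test Protocol 6.1 names, promotes the protocol's additional ANCOVA to primary, and leaves the deciding p-value undefined. Under the best reading the SE is about 0.85 to 0.99 of the correct one and 95% CI coverage about 90 to 95%, with 90% only at the extreme corner. At a mean change near 23 points the LS mean and the t-test give the same decision in every scenario tried. The SDs, slopes and correlations are assumptions, and the mean change and baseline are borrowed from the 24-month per-protocol results. The point should be corrected before analysis, but it is not of must-fix severity.

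**What to change.** In SAP 4.3, 4.4.2 and Table 8, make the one-sample (paired) t-test of ODI change against zero, with its 95% CI, the primary analysis, consistent with Protocol 6.1. Tie p ≤ 0.05 to that test by name. Keep an ANCOVA on mean-centred baseline ODI as supportive, to show how change varies with baseline.

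For pain, in SAP 4.4.3.2 and Table 9, report the mean change with a one-sample t-test and 95% CI, as Table 10 already does at 5+ years. Do not cite Protocol 6.1 as requiring it, and note that no decision rule depends on it.

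The cost is wording and a slightly wider interval: in the nine cases above, a half-width of 3.6 ODI points against 3.0 to 3.5 under the LS mean.

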The primary efficacy endpoint for the original study was the 3-month change in Oswestry Disability Index (ODI) compared between the study arms. This comparison, as previously reported, found that at 3 months the per-protocol (PP) treatment group exhibited a 20.5 Least Squares Mean (LSM) improvement in ODI compared to a 15.2 LSM improvement in the sham group ( $p = 0.019$ ). The PP treatment arm subjects exhibited a durable ODI mean improvement (23.4 points) at 24 months. In terms of percent improvement in ODI from baseline, these results translate into mean percentage improvements of 46.2% at 12 months and 53.7% at 24 months. Responder rates for ODI and low back pain visual analogue scale (VAS) were also maintained through two years, with patients showing clinically meaningful improvements in both: ODI  $\geq$  10-point improvement in 76.4 percent of patients and ODI  $\geq$  20-point improvement in 57.5 percent; VAS  $\geq$  1.5 cm improvement in 70.2 percent of patients. Patients receiving the Intracept Procedure also decreased utilization of opioids and spinal injections as compared to utilization prior to treatment.

The purpose of this study is to measure the long term (5 + years) effectiveness outcomes in subjects treated with the Intracept Procedure in this original SMART study population.

 relevant medsystems	CD_3012_Rev B  Five-Plus Year Follow-Up of SMART Trial Statistical Analysis Plan	Date Effective: November 5, 2019  Page 6 of 21
--	---	---

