### 2.5 Study Assessments

#### ODI

The Oswestry Disability Index (ODI) is a validated questionnaire of low back pain-related disability. It assesses the impact of low back pain on activities of daily living and participation and includes 10 questions. It is scored on a scale of 0 (no disability) to 100 (complete disability), with categories of 0-20 (minimal disability), 21-40 (moderate disability), 41-60 (severe disability), 61-80 (crippling back pain), and 81-100 (bed-bound or exaggerating). The minimally clinically important difference for this tool is considered to be 10 points. For the purposes of this study, this will be administered over the phone.

The ODI score will be calculated as follows:

For each section of six statements the total score is 5; if the first statement is marked the score = 0; if the last statement is marked the score = 5. Intervening statements are scored according to rank. If more than one box is marked in each section, take the highest score.

The ODI score may be summarized as:

$$\text{ODI Score} = \text{total score}/(5 * \text{number of questions answered}) * 100$$

	CD_3012_Rev B Five-Plus Year Follow-Up of SMART Trial Statistical Analysis Plan	Date Effective: November 5, 2019 Page 7 of 21
---	---	---

Scores will be rounded to a whole number for convenience.

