**5+ Year Follow-up Study Endpoints:**

Tables 8 and 9 will be performed for both the ITT (as treated) population and the Intracept treated only population.

Table 8 – Primary Endpoint Results	
	SMART 5+ Yr Follow-up Subjects N = XX Mean ± SD (N), Median [Interquartile Range], Range or % (n/N)
Time of Assessment	
Years since Index Procedure	Mean + SD, Median, Range
Percent with at Least 5 years of Follow-up	% (n/N)
ODI	(N=XX)
Baseline ODI Score (Mean + SD, Median, Range)	Mean + SD, Median, Range
5+ Year ODI Score (Mean + SD, Median, Range)	Mean + SD, Median, Range
Mean change in ODI score from baseline to 5+ Years post-treatment	Mean + SD, Median, Range ( p-value )
ODI Responder Rates	
Subjects with ≥ 10-point ODI decrease	% (n/N) ( p-value )
Subjects with ≥ 15-point ODI decrease	% (n/N) ( p-value )
Subjects with ≥ 20-point ODI decrease	% (n/N) ( p-value )
ODI Response Quartiles	
Subjects with ≤ 24% or less decrease	% (n/N)
Subjects with 25-49% decrease	% (n/N)
Subjects with 50-74% decrease	% (n/N)
Subjects with 75-100% decrease	% (n/N)
	(p-value)

	CD_3012_Rev B Five-Plus Year Follow-Up of SMART Trial Statistical Analysis Plan	Date Effective: November 5, 2019 Page 16 of 21
---	--	---

Table 9 – Secondary Endpoints Results	
	SMART 5+ Yr Follow-up Subjects N = XX
10 Point VAS Numeric Pain Scale	
Baseline VAS Score (Mean + SD, Median, Range)	Mean + SD, Median, Range
5+ Year VAS Score (Mean + SD, Median, Range)	Mean + SD, Median, Range
Mean change in VAS score from baseline to 3 months post-treatment	Mean + SD, Median, Range ( p-value )
VAS Responder Rates	
% of subjects with $\geq$ 1.5 Pt VAS decrease	% (n/N) ( p-value )
% of subjects with $\geq$ 2.0 Pt VAS decrease	% (n/N) ( p-value )
VAS Response Quartiles	
Subjects with $\leq$ 24% or less decrease	% (n/N)
Subjects with 25-49% decrease	% (n/N)
Subjects with 50-74% decrease	% (n/N)
Subjects with 75-100% decrease	% (n/N)
	( p-value )

Table 10 – Regression to the Mean Analysis	
	SMART 5+ Yr Follow-up Subjects N = XX
Regression to the Mean	
Average change in ODI in CONTROL group between baseline and 1 year	Mean, N, 95% CI, t-test p (Ho: $\delta=0$ )
Average change in ODI in CONTROL group between baseline and 2 years	Mean, N, 95% CI, t-test p (Ho: $\delta=0$ )

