Average change in ODI in INTRACEPT group between baseline and 1 year	Mean, N, 95% CI, t-test p (Ho: $\delta=0$ )
Average change in ODI in INTRACEPT group between baseline and 2 years	Mean, N, 95% CI, t-test p (Ho: $\delta=0$ )
Average change in ODI in INTRACEPT group between baseline and 5+ years	Mean, N, 95% CI, rm F-test p (Ho: $\delta=0$ )
Time (per year) effect on ODI in INTRACEPT group	Mean, N, 95% CI, rm F-test p (Ho: time=0)
Average change in VAS in CONTROL group between baseline and 1 year	Mean, N, 95% CI, t-test p (Ho: $\delta=0$ )
Average change in VAS in CONTROL group between baseline and 2 years	Mean, N, 95% CI, t-test p (Ho: $\delta=0$ )
Average change in VAS in INTRACEPT group between baseline and 1 year	Mean, N, 95% CI, t-test p (Ho: $\delta=0$ )
Average change in VAS in INTRACEPT group between baseline and 2 years	Mean, N, 95% CI, t-test p (Ho: $\delta=0$ )
Average change in VAS in INTRACEPT group between baseline and 5+ years	Mean, N, 95% CI, t-test p (Ho: $\delta=0$ )
Time (per year) effect on VAS in INTRACEPT group	Mean, N, 95% CI, rm F-test p (Ho: time=0)

	CD_3012_Rev B Five-Plus Year Follow-Up of SMART Trial Statistical Analysis Plan	Date Effective: November 5, 2019 Page 17 of 21
---	--	---

Table 11 – Comparison of SMART Endpoints			
Characteristic	SMART Treated Subjects in 5+ Yr Follow-up N = XX	SMART Treated Subjects Not in 5+ Year Follow-up N = XX	t-test of Means or Exact Test of Proportions
Change in ODI (Baseline to 3 Months)	Mean + SD, Median, Range	Mean + SD, Median, Range	
Change in VAS (Baseline to 3 Months)	Mean + SD, Median, Range	Mean + SD, Median, Range	
ODI Responders ( $\geq$ point ODI reduction)	% (n/N)	% (n/N)	

Table 12 – Opioids & Injections Utilization	
SMART 5+ Yr Follow-up Subjects N = XX	
Opioid Use	
Subjects Taking Opioids at Baseline	% (n/N)
Subjects actively taking Opioids in last 30 days (5+ Year Follow-up Visit)	% (n/N)
Opioid Dosage (in subjects taking opioids)	
Opioid Dosage at Baseline	Mean + SD, Median, Range
Opioid Dosage at 5+ years post treatment	Mean + SD, Median, Range
Epidural Injections	
Subjects with prior injections at baseline	Mean + SD, Median, Range
Subjects with injections in 12 months prior to 5+ year post treatment visit	Mean + SD, Median, Range
Subjects with injections for low back pain treatment in the same location as Intracept treatment (in the past 12 months):	Mean + SD, Median, Range

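### A p-value of 0.05 or less on ODI change from baseline is allowed to establish durability, though a mean gain of about 3 to 5 points (at assumed SD and n) would meet the rule

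*SAP*

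**What the plan says.** SAP 4.4.2 tests the within-patient mean ODI change from baseline to 5+ years: "The mean change will be analyzed with an ANCOVA with a covariate of baseline ODI score". SAP 4.1 sets the tests at two-sided 0.05. In Table 8 the p-value sits on the row "Mean change in ODI score from baseline to 5+ Years post-treatment", with no confidence interval. If p is 0.05 or less, 4.4.2 permits the conclusion that functional improvement was significant and that "the treatment is durable to mean follow-up for the long term study".

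Other parts of the SAP bear on the same question:

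- The Introduction uses the word for a specific gain: "The PP treatment arm subjects exhibited a durable ODI mean improvement (23.4 points) at 24 months".
- SAP 2.5 gives a yardstick: "The minimally clinically important difference for this tool is considered to be 10 points".
- Table 10 plans "Average change in ODI in INTRACEPT group between baseline and 2 years", the corresponding 5+ year change, and "Time (per year) effect on ODI in INTRACEPT group".
- Table 15 is headed as a durability table and counts subjects whose ODI gain is under 10 points.

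The sentence in 4.4.2 refers to none of these.

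**The concern.** Rejecting zero change from baseline shows that some mean improvement is present at 5+ years. Whether the gain seen earlier was kept is a different question, and it needs a comparison with the earlier gain or a stated amount that must remain. The rule has neither.

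What is at stake is the primary conclusion of the study. Followed exactly, the plan permits a finding of durability after most of the earlier gain has gone and when the mean change is below 10 points. That conclusion could then contradict the responder rates in Table 8, the time effect in Table 10 and the success rate in Table 15, all from the same report.

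**Working it through.** The documents give no SD of change, no power statement and no expected retention, so there is no planned figure to reproduce. The check asks how small an observed mean gain meets the rule.

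**Inputs from the documents.** Two-sided alpha 0.05 (SAP 4.1); at most 133 subjects (SAP 2.1; Table 1 has 132, which makes almost no difference); 23.4-point mean improvement at 24 months, per protocol (SAP Introduction); 10-point important difference (SAP 2.5). SAP 4.4.2 does not write out its null value. Zero change is taken, as Table 10 does.

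**Assumptions.** SD of change 16 to 20, with 12 to 25 as sensitivity; analysed n 67 to 133, about half to all. As a plausibility check, if changes are normal and the 24-month mean and responder rates describe the same subjects, the Introduction's figures imply

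- (23.4 − 10) / z(0.764) = 13.4 / 0.719 = 18.6
- (23.4 − 20) / z(0.575) = 3.4 / 0.189 = 18.0

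**Smallest observed mean gain with p = 0.05.** Formula: t(0.975, n−1) × SD / √n. For example, n = 67 and SD 20 give 1.997 × 20 / 8.185 = 4.88.

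| SD of change | n = 67 | n = 100 | n = 133 |
|---|---|---|---|
| 12 | 2.93 | 2.38 | 2.06 |
| 16 | 3.90 | 3.17 | 2.74 |
| 18.3 | 4.46 | 3.63 | 3.14 |
| 20 | 4.88 | 3.97 | 3.43 |
| 25 | 6.10 | 4.96 | 4.29 |

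At SD 16 to 20 the pass mark is 2.74 to 4.88 points, or 2.74/23.4 = 12% to 4.88/23.4 = 21% of the 24-month gain. Adjustment for baseline lowers it slightly: at SD 18 and n = 133, from 3.09 to between 2.67 and 2.95 for correlations of 0.5 to 0.3. Every entry is below 10.

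**Probability of meeting the rule (noncentral t).**

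| True mean gain | SD 16–20, n 67–133 | SD 25, n = 67 |
|---|---|---|
| 5 points | 0.52 to 0.95 | 0.36 |
| 11.7 points (half of 23.4) | 0.997 or more | 0.965 |

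The rule would therefore almost never separate a kept gain from a half-lost one. For scale only, the Introduction reports a "15.2 LSM improvement in the sham group" at 3 months. That is 15.2/4.88 = 3.1 to 15.2/2.74 = 5.5 times the pass mark.

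**What a direct contrast would show.** Take the paired change from 24 months to 5+ years, with an assumed SD of 12 to 20 and 67 to 133 subjects seen at both visits. The 95% CI half-width is 2.1 to 4.9 points (5.7 at n = 50, SD 20). If 11.7 points had truly been lost, the CI would lie wholly on the side of loss with probability 0.997 or more (0.98 at n = 50, SD 20). For a 5-point loss at SD 20 that probability is only 0.52 at n = 67 and 0.41 at n = 50.

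**The case against.** The best defence is that durable need not mean that the earlier gain was kept. It may mean only that improvement from baseline is still present at the mean follow-up time. The Introduction also attaches the word to a change from baseline, and on that reading the test fits the claim. The verb is permissive, and Tables 8, 10 and 15 would reveal any fading.

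The reading is possible, but it leaves the clause with no content beyond the improvement already concluded, so deleting it costs nothing. If the clause means more, the test does not support it. The permissive verb does not help, because the permission is the defect. The other tables would show a loss, but the conclusion does not depend on them.

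Some of the objection stands. The figure of 3 to 5 points rests on assumed SD and n; the wider range is 2.1 to 6.1 and the probabilities widen with it. The sham result bears on attribution, not on lasting benefit. The paired contrast would often be inconclusive for a moderate loss, which is a reason to report it as an estimate.

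**Conclusion.** The concern holds. The primary test is valid for improvement from baseline, but the durability conclusion attached to it does not follow. Under the stated assumptions an observed mean gain of roughly 3 to 5 points meets the rule, and a half-lost benefit would meet it almost always. The exact pass mark depends on an SD and a sample size that the documents do not give, but it stays below the SAP's 10-point difference throughout the range examined. The logical gap does not depend on these assumptions. The sentence should be corrected before analysis.

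**What to change.** 1. Reword the decision sentence in SAP 4.4.2 along these lines: if p ≤ 0.05 and the mean change is an improvement, it may be concluded that there was a statistically significant mean improvement in ODI from baseline at 5+ years. Delete the durability clause.
2. Base any statement about durability on the paired ODI change from 24 months to 5+ years in subjects with both visits (n, mean, 95% CI). Add it as one row in Table 10 and read it with the Table 10 time effect and Table 15. Report it as an estimate. If the sponsor wants a yes/no use of the word, the SAP must state before analysis which loss the CI has to exclude. No margin is proposed here.

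Two optional tidying steps: show the 95% CI of the mean change in Table 8 (Table 10 already plans it), and align Protocol 6.1, which names Student's t-test with ANCOVA in addition, with SAP 4.4.2, which names only ANCOVA.

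The cost is SAP wording and one table row. No new data are needed, since Table 10 already uses the 2-year ODI. The downsides are a less favourable permitted conclusion and a contrast limited to subjects seen at both visits. The 5+ year ODI is taken by telephone and the documents do not give the 24-month mode, so a mode effect cannot be excluded. The same caution applies to change from baseline.

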9.3 Confidentiality

Subject medical information obtained for this study is confidential, and disclosure to third parties other than those authorized for the study and IRB/regulatory oversight is prohibited. Subjects will be only identified by the unique study number that the subject used during the SMART study. Data will be de-identified in a manner compliant with HIPAA regulations.

Upon the subject's agreement to participate, the independent CRN will schedule and conduct the telephone study visit. Subject's permission for the use of records for supplemental data and data verification purposes will be obtained prior to accessing subject's medical records.

Data generated by this study must be available for inspection upon request by representatives of the FDA, national and local health authorities, the Sponsor or its designee, and the IRB for the study site, if appropriate.

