### 2.3 Study Population

All US subjects that were randomized to the treatment arm of the original SMART Trial will be approached to participate in the long term (5 + year) follow-up study. A single study visit will be performed by an independent nurse CRA to collect the data.

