### **2.6 Endpoint Adjudication**

An independent orthopaedic surgeon will review medical records and radiologic images to determine diagnosis (pain location, etiology, and nature) resulting in an intervention (procedure and/or injections). All interventions will be adjudicated as either a treatment failure (ongoing or exacerbated CLBP of similar location, etiology and nature/severity to the pre-Intratect treatment pain) or not related (different location, etiology, or nature/severity).

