#### 4. STATISTICAL AND ANALYTICAL PLANS

##### 4.1 General Methodology

The SMART Five Plus Year Follow-up Study analysis will be performed when all US SMART treatment arm subjects have been approached to participate in the study, and all subjects who consented to participate, have completed their 5+ year follow-up study visit.

	CD_3012_Rev B Five-Plus Year Follow-Up of SMART Trial Statistical Analysis Plan	Date Effective: November 5, 2019 Page 9 of 21
---	---	---

The number of subjects in the analysis and reasons for withdrawal will be summarized in a CONSORT flowchart. All subjects consenting to participate in the long term follow-up study will be reported as observed. No imputations are planned for missing data.

All statistical processing will be performed by Technomics Research LLC. The standard operating procedures (SOPs) of Tehcnomics Research LLC will be followed in the creation and quality control of all data displays and analyses. Analyses will be conducted using SAS® software Version 9.3 or later unless otherwise stated.

Statistical tests will be two-sided and will be performed at the 0.05 level of significance.

Descriptive statistics will be used for secondary endpoints and will include the number and percentage of subjects in each category. For continuous parameters, descriptive statistics will include n (number of subjects), mean, SD, median, minimum, and maximum. Appropriate inferential statistics will be used for the primary and secondary efficacy variables.

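### No ODI or pain responder rate in SAP Tables 8 and 9 counts a procedure adjudicated as treatment failure as non-response; the planned output bounds that rate but does not report it

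*SAP*

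**What the plan says.** **Main analysis set.** SAP 4.4.2: "The efficacy analysis will be conducted all consented treated subjects with a 5+ year study visit". SAP 4.1 adds "All subjects consenting to participate in the long term follow-up study will be reported as observed", with no imputation.

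**Second cohort.** SAP 4.4.2 compares this set with an "Intracept only treated cohort (with those subjects that had additional procedures such as RF Ablation, microdiscectomy, fusion, etc. removed". Appendix A repeats the pairing: "Tables 8 and 9 will be performed for both the ITT (as treated) population and the Intracept treated only population".

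**Responder rules.** SAP 4.4.3.1 sets ODI thresholds of 10, 15 and 20 points, and SAP 4.4.3.2 sets pain thresholds of 1.5 and 2.0 points. Both depend on score change alone. Table 8 and Table 9 follow them and show each rate as a percentage with n/N.

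**Timing.** SAP 2.3: "A single study visit will be performed by an independent nurse CRA to collect the data". Scores therefore follow any procedure reported at that visit.

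**Adjudication.** SAP 2.6: "All interventions will be adjudicated as either a treatment failure" or as not related. The result enters the composite (SAP 3.1.2, Table 15), which also requires an ODI fall of at least 10, a pain fall of at least 2, no active opioid use and no adjudicated injections.

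**The concern.** In a single-arm durability study, one subject re-treated for the original pain can appear in three ways: as a failure in Table 15, as a responder in the as-treated rate, and not at all in the Intracept-only rate. The Intracept-only rule removes failures and unrelated procedures alike, so it sets aside the distinction that the adjudicator is asked to draw.

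The composite does not settle the question. It merges five criteria, so the effect of procedures on any one threshold cannot be separated. It has no 15- or 20-point ODI version and no 1.5-point pain version. At stake is how much response remains once further surgery for the same problem no longer counts as success.

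**Working it through.** The plan states no re-intervention rate, 5+ year responder target or sample size calculation, so there is no planned figure to reproduce.

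**Notation**, all as shares:
- r: response among subjects with no further procedure (the Intracept-only rate)
- f: observed subjects with a further procedure
- a: those of f with a procedure adjudicated as treatment failure
- s: failures who meet the threshold on their observed scores
- u: subjects with only unrelated procedures who meet it

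**Formulas**
1. Intracept-only = r
2. As-treated = r(1−f) + u·f(1−a) + s·f·a
3. Failure as non-response = r(1−f) + u·f(1−a)
4. Intracept-only n over as-treated N = r(1−f)

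Line 4 needs only planned output. It treats every re-treated subject as a non-responder, so (4) ≤ (3) ≤ (2) at all five thresholds. This holds provided the removal covers every procedure that could be adjudicated a failure. With a = 1, (3) equals (4). With s = 0, (3) equals (2).

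**Inputs.** r = 76.4% (ODI ≥10) and 57.5% (ODI ≥20) are the 24-month rates in SAP 1, borrowed as assumptions. Also assumed: f = 5–20%, a = 50–100%, s = 25–75%, u = r.

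**Example**, r = 76.4%, f = 10%, s = 50%, so r(1−f) = 68.76%:

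| Rate | a = 100% | a = 50% |
|---|---|---|
| Intracept-only | 76.4% | 76.4% |
| As-treated | 68.76 + 0 + 5.0 = 73.8% | 68.76 + 3.82 + 2.5 = 75.1% |
| Failure as non-response | 68.8% | 68.76 + 3.82 = 72.6% |
| Intracept-only n / as-treated N | 68.8% | 68.8% |

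In the first column the planned tables already yield the missing figure. In the second they only place it between 68.8% and 75.1%.

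**Gaps above failure as non-response**
- Intracept-only, r·f·a. For r = 76.4%: 3.8 to 15.3 points over f = 5–20% with a = 1, and 1.9 to 7.6 with a = 0.5. For r = 57.5%: 2.9 to 11.5 and 1.4 to 5.8.
- As-treated, f·a·s. At f = 10% and a = 1: 2.5, 5.0 or 7.5 points for s = 25, 50 or 75%.

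**Sensitivity to the anchor.** Suppose 76.4% is instead the as-treated rate p, all removed subjects are failures, and their response pf runs from 0 to p. Then failure as non-response is p − f·pf and Intracept-only is (p − f·pf)/(1−f).
- f = 10%: failure as non-response 68.8 to 76.4%, Intracept-only 76.4 to 84.9%. The Intracept-only gap is 7.6 to 8.5 points and the as-treated gap 0 to 7.6.
- f = 20%: the Intracept-only gap is 15.3 to 19.1 points and the as-treated gap 0 to 15.3.

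**The case against.** The strongest reply is that little is hidden. Tables 8 and 9 give n/N in both cohorts, so a reader can form the lower bound at every threshold. Table 13 describes procedures by type, level and timing. Table 15 reports adjudicated re-intervention and a composite that counts it as failure. ODI 15 and 20 are not listed endpoints in SAP 3.1.2; they appear only in SAP 4.4.3.1 and Table 8. SAP 4.4.2 already makes all consented subjects with a visit the efficacy set, and the SAP does not present the Intracept-only cohort as the main one.

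Most of this stands, and it sets the priority. What remains is that the bound is not labelled, the reader must build it from two tables, and the exact rate stays unknown when some procedures are unrelated. Tables 13 and 15 count procedures but do not cross them with response at each threshold.

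A second reply is that the sizes rest on assumed inputs. This is correct. SAP 1 does not say whether its 24-month rates exclude re-treated subjects, and the gaps change with the cohort to which those rates are assigned.

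A reader might also infer that the primary result is biased or that failures are dropped from it. The documents do not support that. The primary ANCOVA uses all consented treated subjects with a visit, on observed scores, which is a legitimate treatment-policy summary.

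**Conclusion.** The point holds as a missing sensitivity analysis. No responder row in Tables 8 and 9 treats an adjudicated failure procedure as non-response, and the Intracept-only rates are selected on a post-treatment event. It would go too far to say that planned output leaves the figure unknown: it is bounded, and it is exact if every re-treated subject is a failure.

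Under the assumptions above with r as the Intracept-only rate, that rate exceeds failure as non-response by 1.4 to 15.3 points across the two ODI thresholds. The as-treated excess is zero if no failure meets the threshold. These figures show possible scale only and are not estimates for this study. The as-treated mean change, the primary test and its decision rule are unaffected. Priority is low.

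**What to change.** **Reconcile first.**
- The treatment-failure wording. SAP 2.6 asks for similar location, etiology and nature or severity. SAP 3.1.2 and the success definition under Table 15 ask for the same location, etiology and severity. The re-intervention row of Table 15 names location and etiology only.
- The pain window. SAP 4.4.3.2 and the mean-change row of Table 9 refer to 3 months, whereas SAP 3.1.2 refers to 5+ years.

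**Then add**, for all observed subjects, one sensitivity responder row per planned threshold (ODI ≥10, 15, 20; pain ≥1.5, 2.0). A subject with a procedure adjudicated as treatment failure is a non-responder. Subjects with only unrelated procedures keep their observed scores. Limit the rows to procedures, which are captured for the whole period since Intracept; injections are captured for 12 months only and are already in the composite.

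**State** that the Intracept-only rates are conditional on no further procedure and are not the main estimate.

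**Cover procedures that cannot be adjudicated.** SAP 2.6 relies on records: "An independent orthopaedic surgeon will review medical records and radiologic images to determine diagnosis". Under Protocol 9.3 the subject's permission "will be obtained prior to accessing subject's medical records", so some records may be unavailable. Use one rule for these cases in the new rows and in Table 15, so that no subject is a composite success and a non-responder for this reason alone, and report their number.

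**Cost.** A few lines of SAP text, five rows and minor programming, using adjudication already planned. The sensitivity rates may look somewhat less favourable. The as-treated mean change stays on observed scores.
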